End of treatment visit (EOT) will take place 30 + 2 days after the last dose of ipilimumab. This visit will require a complete evaluation of patient's symptoms, Karnofsky/Barthel scores, physical exam (including weight, vital constants and neurological exam), lab tests, collection of AEs and of concomitant medication. If the disease was not evaluated before, EOT visit should include a body and cranial CTscan/MRI.

6.2.1.e Follow-up visits.

Per protocol, the disease should be evaluated until death or confirmed progression (mWHO/immune response criteria). Tumor assessment will be performed with CT/MRI of brain, chest, abdomen and pelvis at baseline, at weeks 12 and 17 \pm 1 and then, every 9 \pm 1 weeks. The same method of assessment (CT or MRI) should be used throughout the patient's time on study for consistent evaluation of response.

After EOT visit, the occurrence of new SAEs and irAEs will be reported up to 90 days after last ipilimumab administration. Ongoing SAEs/irAEs will be followed up until recovery.

Survival status will be checked at week 12, 16-18 and then, every 8-10 weeks.

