6.4.2. Efficacy Evaluation

The primary endpoint will be 1-year survival. Secondary endpoints require the assessment of disease progression or response to therapy.

Secondary response-based endpoints (PFS, BORR, DCR, and duration of response) will be captured using two distinct but related criteria:

- Modified WHO (mWHO) criteria.
- Immune-related Response Criteria (irRC)

The mWHO criteria will be used to define response-based secondary endpoints. The irRC will be used to a) define exploratory endpoints and to b) define confirmed disease progression for the purpose of discontinuing ipilimumab treatment in order to permit physicians to continue treating with ipilimumab in spite of the appearance of small new lesions and/or transient increases in tumor burden that may signal anti-cancer inflammation. The irRC criteria will be used for exploratory analyses. Tumor response will be based on investigator assessment.

Tumor assessment of the disease will be performed with CT/MRI of brain, chest, abdomen and pelvis at baseline, at weeks 12 and 16-18 and then, every 8-10 weeks. The same method of assessment (CT or MRI) should be used throughout the patient's time on study for consistent evaluation of response.

6.4.2.a Radiological Assessment of Tumor Lesions

CT/MRI imaging of the brain, chest and abdomen-pelvis is required at Screening (ie, Baseline) and at each tumor assessment visit, regardless of the location of known metastases. In addition, CT/MRI scans must be obtained of anatomic regions not covered by the chest and abdomen scans, in subjects where there is clinical suspicion for deep soft tissue metastases (eg, lesions in the thigh). Such additional CT/MRIs will be required at Screening only when deep soft tissue disease is suspected during Screening and must be consistently repeated at all tumor assessment visits if a deep soft tissue lesion is identified during Screening. In cases without suspicion for deep soft tissue disease, no such CT/MRIs are required.

Obviously, brain scans are required at Screening and at each disease evaluation visit. MRIs are preferred, contrast-enhanced CTs are a second choice.

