- Progressive Disease (PD): Appearance of any new lesion(s) and/or unequivocal progression of non-index lesion(s) (eg, an increase in pleural effusions, or other fluid collections defined as an approximate doubling of the volume which was present at baseline or nadir, unless there is radiographic evidence of a benign cause for the fluid collection or the effusion is cytologically negative for malignant cells).

6.4.2.f Response per Time Point

OR is determined as the combination of assessments of index and non-index lesions using the following criteria presented in Table 13

Table 13: Overall Response per mWHO

Index Lesions	Non-index Lesions	New Lesions	Overall Response
CR	CR	No	CR
CR	IR/SD	No	PR
PR	CR or IR/SD	No	PR
SD	CR or IR/SD	No	SD
PD	Any	Yes or No	PD
Any	PD	Yes or No	PD
Any	Any	Yes	PD

6.4.2.g Best Overall Response (BOR)per Subject (Including all TimePoints)

BOR is the best confirmed response designation over the study as a whole, recorded between the date of first dose until the last tumor assessment prior to subsequent therapy (except for local palliative radiotherapy for painful bone lesions) for the individual subject in the study. The assessment of response at 12 weeks has particular emphasis due to the mechanism of action of ipilimumab inducing immune responses as basis for clinical responses. For the assessment of BOR, all available assessments per subject are considered. CR or PR determinations included in the BOR assessment must be confirmed by a second (confirmatory) evaluation meeting the criteria for response and performed no less than 4 weeks after the criteria for response are first met.

Consistent with the definition of BOR in this study, the date of disease progression is defined for each subject based on post-Week 12 time points, in cases where a subject had an OR of CR, PR or SD at Week 12. BOR assessment of SD requires an OR of SD (or unconfirmed PR or CR) at Week 12, in the absence of BOR of CR, PR or PD.

The following criteria (Table 14) summarize the combination of assessments of OR at different time points throughout the study to establish BOR for the individual subject with emphasis on the 12 week time point due to the mechanism of action of ipilimumab:

Table 14. Assessment of Best Overall Response

Overall Response At Time Points Before Week 12	Overall Response At Week 12	Overall Response At Time Points After Week 12	Best Overall Response For All Time Points
CR* or PR*	Any	Any	CR or PR (at time point before Week 12)

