PD, SD, or no data	CR* or PR*	Any	CR or PR (at 12 weeks)
PD, SD, CR**, PR** or no data	SD, CR**, PR**	CR* or PR*	CR or PR (at time point after Week 12)
PD, SD, PR**, CR** or no data	SD, PR**, CR**	PD, SD, PR**, CR** or no data	SD
SD, PR**, CR** or no data	PD	Any	PD (at Week 12)
PD	PD	Any	PD (at time point before Week 12)

* Initial OR of PR or CR confirmed by a second (confirmatory) evaluation meeting the criteria for response and performed no less than 4 weeks after the criteria for response are first met.

** OR of PR or CR not confirmed by a second (confirmatory) evaluation meeting the criteria for response and performed no less than 4 weeks after the criteria for response are first met.

6.4.2.h Local Radiotherapy for Symptomatic Bone Lesions

Local radiation treatment to the site of bone metastasis will be permitted for palliative pain management at any time during the study but it is encouraged that the Investigator perform this local radiotherapy following consultation with the Medical Monitor and the Week 12 following re-staging assessments (ie, Week 16, confirmatory assessments).

6.4.2.i Response Kinetics and Immune-related Endpoints

Ipilimumab is expected to trigger immune-mediated responses, which require activation of the immune system prior to the observation of clinical responses. Such immune activation may take weeks to months to become evident. Some subjects with advanced melanoma may have objective volume increase of tumor lesions within 12 weeks following start of ipilimumab dosing. These subjects may not have had sufficient time to develop the required immune activation or, in some subjects, tumor volume increases may represent infiltration of lymphocytes into the original tumor. In conventional studies, such tumor volume increases during the first 12 weeks of the study would constitute PD and lead to discontinuation of imaging to detect response, thus disregarding the potential for subsequent immune-mediated clinical response. Therefore, in this study, subjects with tumor volume increase detected prior to Week 12 but without rapid clinical deterioration will continue to be treated with ipilimumab and clinically observed with a stringent imaging schedule to allow detection of a subsequent tumor response until progression is confirmed at the subsequent timepoint. Such assessments will be using identical criteria, considering

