At each subsequent assessment timepoint, a separate assessment of timepoint overall response will be obtained for that timepoint. The sum of products of perpendicular diameters calculated and recorded at each post-baseline timepoint for immune-related response purposes (irSPD) include measurements of index lesions and also include measurable new lesions which are not too small to measure at this timepoint. A value of 25 mm² (5 mm x 5 mm) is imputed for each index and previously measurable new lesion which is present but too small to measure.

Timepoint Overall Response using irRC

The overall assessment of immune-related response reported at each timepoint will be based on the following criteria:

- **Immune-related Complete Response (irCR):** Complete disappearance of all tumor lesions (index and non-index together with no new measurable/unmeasurable lesions).
- **Immune-related Partial Response (irPR):** A decrease, relative to baseline of the irSPD (as defined above) of 50% or greater is considered an irPR.
- **Immune-related Stable Disease (irSD):** irSD is defined as an evaluable response that fails to meet criteria for immune-related complete response or immune-related partial response, in the absence of immune-related progressive disease.
- **Immune-related Progressive Disease (irPD):** At least a 25% increase in the irSPD (based on irSPD of all index lesions and any measurable new lesions, as defined above) over the nadir irSPD, or the occurrence of any new measurable lesions if the SPD nadir is “0”.

- **Immune-related Unknown Response (irUN):** Tumor assessments which cannot be evaluated (eg, due to image quality, inability to assess all relevant lesions, etc) will be reported as irUN.

Immune-related Response Criteria Definitions are summarized in Table 15.

Table 15. Immune-related Response Criteria Definitions

Index Lesions	Non-index Lesions	New Lesions	% Change in Tumor Burden (including new lesions)	Overall irRC Response
CR	CR	No	- 100%	irCR
CR	Any	Any	>-100% to ≤ -50%	irPR
			> -50% to < +25%	irSD
			≥ +25%	irPD
PR	Any	Any	> -100% to ≤ -50%	irPR
			> -50% to < +25%	irSD
			≥ +25%	irPD
SD	Any	Any	> -50% to < +25%	irSD
			≥ +25%	irPD
PD	Any	Any	≥ +25%	irPD
U	Any	Any	U	irUN

Note: Both immune-related response and progression require confirmation through a subsequent scan at least 4 weeks apart from first detection.

6.4.2.k Immune-Related Best Overall Response Using irRC (irBOR)

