irBOR is the best confirmed irRC overall response over the study as a whole, recorded between the date of first dose until the last tumor assessment before subsequent therapy (except for local palliative radiotherapy for painful bone lesions) for the individual subject in the study. For the assessment of irBOR, all available assessments per subject are considered.

irCR or irPR determinations included in the irBOR assessment must be confirmed by a second (confirmatory) evaluation meeting the criteria for response and performed no less than 4 weeks after the criteria for response are first met.

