1.5.3. BEST RESPONSE (Evaluable)

Following the protocol, for the efficacy analysis the population of was used evaluable patients: $n = X$ (see section 1.1)

Table 34. Best response (Evaluable)

		N (%; 95% CI)
Best response (Criteria modified from WHO)	CR	
	PR	
	EE	
	PE	
	NE (Not evaluated)	
	Total	
Best response (Response Criteria related to immunity. CRri)	RCri	
	RPri	
	EEri	
	PEri	
	NEri (Not evaluated)	
	Total	

According to protocol: Overall best response rate (TMRG)

The MRG is defined by a population subgroup as the total number of patients treated in the subgroup whose MRG is CR or PR, divided by the total number of patients treated in the subgroup.

Table 35. TMRG (Evaluables)

		N (%; 95% CI)
TMRG: CR or PR (Modified WHO Criteria)	No	
	Yes	
	Not evaluated	
	Total	
TMRG: CR or PR (Response Criteria related to immunity. CRri)	No	
	Yes	
	Not evaluated	
	Total	

According to protocol: Disease control rate (TBI)

TBI is defined as the total number of patients treated in each subgroup whose GRM is CR, PR or EE, divided by the total number of patients treated in the subgroup.

Table 36. TBI (Evaluable)

		N (%; 95% CI)
TCE: CR or PR or EE (Modified WHO Criteria)	No	
	Yes	
	Not evaluated	
	Total	
TCE: CR or PR or EE (Response Criteria related to immunity. CRri)	No	
	Yes	
	Not evaluated	
	Total	

Table 37. Time to best response (evaluable)

	N ¹	Mean (SD)	Median (Min-Max)
Time to best WHO response (months from 1st cycle of ipilimumab)			
Time to best response CRri (months from 1st cycle of ipilimumab)			

1: Patients with response recorded in CRDe

Table 38. Time to best response (Evaluable) according to MRG

Time to best response	N ¹	Mean (SD)	Median (Min-Max)
Best global response (modified WHO criteria)	CR		
	PR		
	EE		
	PE		
Time to best response	N ¹	Mean (SD)	Median (Min-Max)
Best Overall response (Response Criteria related to immunity. CRri)	RCri		
	RPri		
	EEri		
	PEri		

1: Patients with response recorded in CRDe

According to protocol: Duration of response

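### Stable disease must be seen at Week 12 under mWHO but at no minimum time under irRC, so the irRC disease control rate can exceed the mWHO rate partly by definition

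*Protocol*

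**What the plan says.** **mWHO.** Protocol section 6.4.2.g states: "BOR assessment of SD requires an OR of SD (or unconfirmed PR or CR) at Week 12". Table 14 applies this: stable disease before Week 12 followed by progression at Week 12 gives a best response of PD.

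**irRC.** Section 6.4.2.j defines stable disease at each timepoint: "irSD is defined as an evaluable response that fails to meet criteria for immune-related complete response or immune-related partial response", in the absence of irPD. It sets no minimum time or duration. Section 6.4.2.k runs irBOR from the first dose to the last assessment before subsequent therapy and says "For the assessment of irBOR, all available assessments per subject are considered". The only added condition is "irCR or irPR determinations included in the irBOR assessment must be confirmed by a second (confirmatory) evaluation meeting the criteria for response". There is no irRC counterpart to Table 14.

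**Reporting.** Section 9.3.2.3 gives a single definition of disease control rate (CR, PR or SD). SAP Table 36 applies it to mWHO and then to a row labelled "TCE: CR or PR or EE (Response Criteria related to immunity. CRri" (EE is stable disease, TCE the disease control rate). SAP Table 40 likewise reports duration of stable disease under both criteria from one definition.

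**Scan timing.** Section 6.4.2 schedules imaging "at baseline, at weeks 12 and 16-18 and then, every 8-10 weeks". Section 6.4.2.c also allows extra assessments when progression is suspected. Section 6.2.1.d says of the End of Treatment (EOT) visit: "If the disease was not evaluated before, EOT visit should include a body and cranial CTscan/MRI".

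**The concern.** The two rates in SAP Table 36 look like one quantity measured by two criteria, but their thresholds for stable disease differ in a way that has nothing to do with immune response kinetics. Section 1.3.5.a justifies irRC as capturing benefit that conventional criteria may miss, so a reader will naturally take a higher irRC rate as that benefit. If some of the excess is irSD seen only before Week 12, that part of the gap is produced by the definition, and it always favours irRC. In Table 40 the same patients would add short durations to the irRC row, under a definition (section 9.3.2.5) that itself refers to stable disease at Week 12.

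**Working it through.** **1. Plan's own figures.** The documents state no design figure for the disease control rate. The only one is for the primary endpoint (section 9.1): at least 17 one-year survivors among 56, 20% versus 35%. The exact binomial gives one-sided alpha 0.043 and power 0.806, so it reproduces. It supplies n = 56 and is otherwise unaffected.

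**2. The two rule sets applied to the same patients.**

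| Course | mWHO best response | irBOR as written | irBOR with the fix |
|---|---|---|---|
| Stable before Week 12, progression at Week 12 | PD (Table 14) | irSD: disease control | irPD |
| Stable before Week 12, death before Week 12 | Cannot be SD (6.4.2.g) | irSD: disease control | Not evaluable, counted as failure |
| No scan, death before Week 12 | No assessment | No assessment | No assessment |
| Progression before Week 12, stable at Week 12 | SD (Table 14) | irSD | irSD |
| Progression at Week 12, unconfirmed under irRC, then stable at weeks 16-18 | PD (Table 14) | irSD | irSD |

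The first two rows are the problem. The fourth shows that mWHO also counts some early progressors. The fifth is the kind of difference irRC is meant to show, and the fix keeps it.

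**3. Where an irSD before Week 12 could come from.** The first scheduled post-baseline scan is at Week 12, which leaves two routes.
- Unscheduled scans on suspicion of progression (6.4.2.c).
- The EOT scan of a patient who stops ipilimumab early, if 6.2.1.d is read literally. With doses on days 1, 22, 43 and 64, and EOT 30 to 32 days after the last dose:
  - last dose 1: days 31-33, weeks 4.4-4.7
  - last dose 2: days 52-54, weeks 7.4-7.7
  - last dose 3: days 73-75, weeks 10.4-10.7
  - last dose 4: days 94-96, weeks 13.4-13.7

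**4. Size.** Each affected patient moves the irRC rate by 1/56 = 1.8 points. Illustration with assumed counts and exact 95% intervals:
- 14/56 = 25.0% (14.4 to 38.4), no patient with irSD only before Week 12
- 17/56 = 30.4% (18.8 to 44.1), three such patients
- 19/56 = 33.9% (21.8 to 47.8), five such patients

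The base of 14 is an assumption, close to the 26.4% mWHO rate at 3 mg/kg in protocol Table 10.

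**5. Can the count be derived?** No. Assuming exponential survival, the share dead by Week 12 is 1 − S^(84/365.25), where S is one-year survival. This is 21% (12 of 56) at S = 35% and 31% (17 of 56) at S = 20%. Those figures only cap the early deaths that could count under that assumption. A patient who dies without a scan has no irRC assessment and belongs in the Not evaluated row of Table 36.

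**The case against.** **Early scans may be rare.** In protocol Table 12 the EOT column is headed C4D30, and its scans carry note 5, which places them at week 12+1. Section 3 says all subjects who enter treatment, including those who stop for drug-related adverse events or show clinical progression, should have a 12-week tumour assessment. Read together, the EOT scan in 6.2.1.d may be only a catch-up for a missed Week 12 scan. This stands as a serious qualification: a reader might infer that the protocol routinely generates early scans, and the documents do not settle that. What clearly remains is the unscheduled scan, done on suspicion of progression in patients less likely to show irSD.

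**A figure of several points is not supported.** A reader might infer one as follows. Take 61% completing four doses in MDX010-20, so 39% stopping early; spread the stops evenly over doses 1 to 3; assume exponential PFS with a median of 1.5 to 2.8 months. The irRC rate then rises by 6-7 points, or 3-4 points if 20% stop early. The arithmetic is right but the inputs fail:
- The 61% is of randomised patients. With 540 randomised and 131 + 380 = 511 treated, 0.61 × 540 / 511 = 64% of treated patients completed, so about 36% stopped early.
- Patients who stop early are given average PFS, although many stop because they deteriorate.
- SAP Table 36 covers evaluable patients, who must have completed WBRT. That removes some patients who stop after dose 1, the group contributing most.
- The even spread and the 1.5-month median have no source in the documents.

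**Confirmation.** Section 6.4.2.k calls irBOR the best confirmed response, which might be stretched to cover irSD. The text spells out confirmation only for response and progression, so this does not close the gap. It does matter for the fix: irPD needs a second scan at least 4 weeks later, so one irPD scan before death is not confirmed progression.

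**Low stakes.** Sections 6.4.2 and 9.3.2 make irRC endpoints exploratory. The irRC response rate listed as secondary in section 2.2 rests on CR and PR, which already need confirmation. Disease control rate is not a listed objective, and no test compares the two rates. All of this stands.

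**Conclusion.** The asymmetry is in the text. Applied as written, the irBOR rule lets an irSD seen only before Week 12 count as disease control, and SAP Tables 36 and 40 set the result beside an mWHO figure that excludes it. The bias can only raise the irRC disease control rate.

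A reader might infer that the irRC rate generally counts patients who had progressed or died by Week 12. The documents do not support that. It happens only to a patient with an irSD scan before Week 12, and early progression as such does not separate the two criteria.

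The number affected is unknown; the one firm figure is 1.8 points per patient at n = 56. At the 26.4% reference rate the standard error is √(0.264 × 0.736 / 56) = 5.9 points, so one or two such patients would sit well inside sampling error. With an exploratory, unpowered endpoint and no effect on the primary analysis, this is a cheap improvement rather than a threat to the trial's conclusion.

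**What to change.** - In section 6.4.2.k, state that an irBOR of irSD requires irSD, or an unconfirmed irPR or irCR, at or after the Week 12 assessment. The words *or after* keep late stabilisation that follows an unconfirmed irPD.
- State how a patient with irSD only before Week 12 is classified: irPD if irPD follows, otherwise not evaluable. Say explicitly how an unconfirmed irPD before death or loss to follow-up is handled. In either case the patient stays in the denominator and counts as a failure for the irRC disease control rate.
- Apply the same rule in SAP Tables 34, 36 and 40.
- Reconcile the EOT imaging text in 6.2.1.d with Table 12 note 5 and the 12-week assessment in section 3, so that it is clear which early scans are expected.

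The cost is one protocol sentence with its classification rule, and one programming rule in the SAP. No new data are needed. The downside is a slightly lower irRC disease control rate.

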6.4.3. Exploratory endpoints: predictive biomarkers

6.4.3.a Background for Biomarker Research in Melanoma

Despite advances in our knowledge of the disease, malignant melanoma remains an unpredictable entity. Biomarkers are playing an increasing role in the development of new cancer treatments. Predictive biomarkers can be used to improve response rate, by subject stratification and support treatment discontinuation decision in case of severe adverse events. Biomarkers also add to the knowledge on the mechanism of action of drugs, supporting rationale for different combination therapies and dosing schedules.

An area of unmet need in melanoma drug development is the identification of biomarkers that can be used to reliably predict or assess whether systemic therapies would provide benefit to subjects. The revolution in molecular biological techniques, such as DNA sequencing and gene-expression profiling, has

uncovered many potential protein targets and biomarkers relevant to melanoma progression. The elucidation of biomarkers in melanoma, both diagnostic and prognostic, is an important area for investigation.

Previous Ipilimumab studies have explored a variety of predictive and pharmacodynamic biomarkers in melanoma subjects and resulted in the identification of a number of potential biomarker candidates that might be used to better understand the mechanism of action of Ipilimumab and to predict or early predict (by measuring changes within few weeks after the start of the treatment) response to this agent. These include peripheral blood biomarkers such as Absolute Lymphocyte Count (ALC), activated and memory T cells, and some serum biomarkers such as C-reactive protein (CRP). An apparent association was detected between low baseline serum levels of CRP and longer overall survival in metastatic melanoma subjects treated with 10 mg/kg ipilimumab in CA184007 Phase 2 trial. Gene polymorphisms of CD86 and CTLA-4 have been associated with a number of autoimmune diseases. Previously, the association of some of these genetic markers with efficacy or safety of ipilimumab has been explored. However, data from limited number of subjects from Phase 2 trials with ipilimumab have not yet resulted in the discovery of any genetic biomarkers that might predict efficacy or immune-mediated adverse events caused by this agent.

The aim of this optional study is to determine whether a correlation between the proposed biomarkers and disease behavior (progression, overall survival, treatment response) exist in patients with melanoma metastatic to the brain, that have specifically consented for the participation in this part of the study.

The present biomarker plan proposes assessment of such biomarkers to investigate their associations with immune-mediated adverse events when ipilimumab is administered with radiation therapy:

- To evaluate tumor biomarkers pathways by IHC and their correlation with prognosis as well as their role as predictive factors to treatment with ipilimumab+radiotherapy in 29 patients participating on GEM 12-02 clinical trial.
- To evaluate serum levels of several cytoquines (by means of cytoquines panel) at baseline, and before each ipilimumab administration (expected 4-5 samples per patient, 29 patients).
- To evaluate Peripheral Blood Mononuclear Cells (PBMCs), with true counts for absolute numbers and percentage at baseline, and before each ipilimumab administration (expected 4-5 samples per patient, 29 patients).

6.4.3.b Biomarker Measures

- ALC will be assessed as a part of standard hematology panel.
- CRP will be obtained as a component of the serum chemistry lab test.
- Tumor Samples: at least 29 tumor samples (biopsies) will be collected and histology and IHC will be carried out to evaluate a panel of biomarkers that includes: CD3, CD4, CD8, CD31, PD-1, PD-L1, CD45RO, CD68, NK, DC, CD80, CD86, ICAM, VCAM, HLA-A,B,C, HLA-DR, PTEN.
- Serum Samples will be evaluated in at least 29 patients at 4-5 timepoints (116 refrigerated serum samples). For each sample, 10 ml of serum will be collected and a cytokine panel will be carried out, including:

Cytokines			
IFN- γ	TNF- α	IL-1 β	IL-2
IL-4	IL-6	IL-7	IL-8

IL-10	IL-12	IL-15	IL-17
Adhesion molecules			
sICAM-1	sVCAM-1	sCD25	

- Peripheral Blood immune cells will be evaluated in at least 29 patients at 4-5 timepoints (116 refrigerated peripheral blood samples). For each sample, 10 ml of heparin blood will be collected for flow cytometry to evaluate a panel of cells that include:

T cells			
CD3	CD4	CD8	CD56
CD45RA	CD45RO	CD62L	LFA-1 (activated conformation)
NK cells			
NKp46	CD16	CD56	
T reg			
CD4	CD25	FoxP3	
MDSC			
CD14	CD15	CD33	HLA-DR
DC			
BDCA-1	BDCA-2	BDCA-3	
T cell activation (with PMA + ionomycin)			
CD69	CD25	IFN-	IL-4
IL-17	LFA-1(active conformation)		

If consented by the patient, the remaining biological materials (tissue blocks or its derivatives, serum aliquots and frozen pellets) will be stored for future studies.

Biological samples for the these exploratory studies will be collected by

[REDACTED]

[REDACTED]

[REDACTED]

[REDACTED]

[REDACTED]

[REDACTED]

[REDACTED]

The molecular substudy coordinator is Dr. [REDACTED]

Samples will be analyzed and stored in

[REDACTED]

[REDACTED]

[REDACTED]

[REDACTED]

An additional document will be provided in the Investigator Site File with detailed instructions for biological sample collection and shipment.

6.4.3.c. Blood/Lab Biomarkers timepoints

Except for ALC and RCP, which will be determined with every routine blood tests as per section 6.4.1.e and Table 12, the other biomarkers will be sampled at baseline (i.e. up to 28 days prior to C1D1), at C1D21, C2D21, C3D21 (+/- 3 days), and at the EOT visit.

6.4.3.d Archival Tumor Tissue

When available, paraffin-embedded tumor tissue will be submitted for each subject for immunoscore. The tumor tissue does not have to be submitted prior to the start of treatment and is not required for eligibility. Separate instructions for submission of archival tumor samples will be provided.

